6.12 Multiplicity

For the primary and secondary endpoints, the treatment comparisons subject to control of the false positive rate will be 3.2 mg lofexidine vs. placebo and 2.4 mg lofexidine vs. placebo. Comparisons of 3.2 mg vs. 2.4 mg will be descriptive. The familywise error rate (FWE) for the collection of primary and secondary endpoint comparisons will be controlled at the 0.05 level, two-sided, by a sequential testing strategy in which hypotheses are tested in the following order, each at the 0.05 level, using a two-sided test.

- 1. Primary: AUC(1-7), 3.2 mg lofexidine versus placebo;
- 2. Primary: AUC(1-7), 2.4 mg lofexidine versus placebo;
- 3. Secondary: Completion rate, 3.2 mg lofexidine versus placebo; and
- 4. Secondary: Completion rate, 2.4 mg lofexidine versus placebo.

The tertiary/exploratory endpoints will be tested without multiplicity adjustment.

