6.14 Change to Planned Protocol Analysis

The following changes have been made to the planned protocol analyses sections:

Section 17.2.7 Control of the False Positive Rate and Statistical Testing Strategy

Change: All statistical tests will be two-sided at the 0.05 significance level. This is a change from the protocol, where it was specified that statistical tests would be one-sided at the 0.025 significance level.

Reason: Two-sided statistical tests at the 0.05 significance level is statistical convention for hypothesis testing.

Section 17.2.8.1 SOWS-Gossop AUC (1-7)

Change: A number of sensitivity analyses have been added and are detailed in section 16.9.2 of the statistical analysis plan.

Reason: To provide additional sensitivity analyses of log_e (SOWS-Gossop score +1) from day 1 to day 7 under differing mechanisms for missing data, including Missing at Random (MAR) and Missing Not at Random (MNAR)

Section 17.2.8.2 Completion Status

Change: A logistic regression model including fixed effects for treatment group, gender and site will be used instead of a Cochran-Mantel Haenszel test to test for a difference in completion status between the 2 Lofexidine groups and placebo.

Reason: To additionally adjust for site in the analysis and to provide an interpretation of the effect of treatment using odds ratios.

Sections: 17.2.8.3 SOWS-Gossop on Days 1, 2, 3, 5, 6 and 7 and 17.2.8.4 OOWS-Handelsman, MCGI (Subject and Rater), VAS-E, and COWS

Change: A MMRM model will be used to test for a difference in the log_e (SOWS-Gossop score +1) at each of days 1 through 7 between the 2 Lofexidine groups and placebo. This replaces planned pattern-mixture approach used in the principal analysis.

Reason: MMRM model is a standard approach for the analysis of treatment differences at different time points when there are repeated measures.

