Certain efficacy variables are not measured at baseline. The MCGI Subject and Rater scales are each sub-divided into two components.

Effective: 24-Dec-2014

Page 11 of 29

Change 12

Section 6.11 Tertiary/Exploratory Endpoints

The text in bold was amended for Retention Analysis (Time to Removal from Study Treatment):

Time to removal from study treatment is defined as the last study day on which the subject received treatment. A completer for the purpose of this analysis is defined as a subject receiving at least 1 dose on Day 7 and the having the SOWS assessment completed. This will be based on the flag indicating the subject completed the double-blind phase as recorded on the CRF. The time to removal from study treatment for completers will be censored on Day 7. The time to removal from study treatment for subjects who complete some treatment on Day 7 but who do not satisfy the definition of completer will be Day 7, uncensored.

This endpoint will be summarized descriptively for each combination of treatment group and gender with Kaplan-Meier curves and tabulations of the number and percentage of subjects newly removed from receiving study treatment on each of study Days 1 to 7. Each Lofexidine dose group will be compared inferentially to placebo with a Cox proportional hazards regression model of time to removal from study, including covariates for treatment and sex. If the Cox proportional hazards model does not converge, then the covariate sex will be dropped from the model and the Cox proportional hazards regression model will be stratified by sex instead. The estimated hazards ratio will be reported as a descriptive measure along with the associated 95% confidence interval.

Justification

To make the definition clearer of what constitutes a completer for this analysis and to redefine the censoring algorithm accordingly. The primary analysis no longer includes site in the model; therefore site has been removed as a variable from all subsequent statistical models.

Change 13

Section 6.11 Tertiary/Exploratory Endpoints

The text in bold was added.

Concomitant Medication Analysis

Effective: 24-Dec-2014

Page 12 of 29

For each of Days 1 to 7, each subject's number of concomitant medication taken will be treated as a continuous variable. Descriptive statistics will be provided on the as-observed data on each study day and also overall study days.

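### The exploratory retention Cox model runs on whole-day times with at most seven values and names no tie method; under the Breslow approximation the hazard ratio would be pulled modestly toward 1

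*SAP*

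**What the plan says.** Change 12 of SAP Addendum 1 replaces the retention text of SAP Section 6.11 and is the current wording.

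- Time scale: "Time to removal from study treatment is defined as the last study day on which the subject received treatment". The unit is the study day.
- Range: the tabulation counts "subjects newly removed from receiving study treatment on each of study Days 1 to 7", so there are at most seven distinct values.
- Censoring: "The time to removal from study treatment for completers will be censored on Day 7". A Day 7 event needs a subject who was dosed that day but did not meet the completer definition.
- Model: a "Cox proportional hazards regression model of time to removal from study, including covariates for treatment and sex", with stratification by sex as the fallback if it does not converge.
- Reporting: "The estimated hazards ratio will be reported as a descriptive measure along with the associated 95% confidence interval". The same paragraph calls the comparison of each dose with placebo inferential.
- Status: SAP Section 6.14 sets the level ("All statistical tests will be two-sided at the 0.05 significance level"), and Section 6.12 adds: "The tertiary/exploratory endpoints will be tested without multiplicity adjustment".

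SAP Section 6.1 names SAS 9.3 or higher. No tie method for the Cox model appears in Protocol Section 17.2.8.5, SAP Section 6.11, Addendum 1 or Addendum 2. The only tie rule anywhere concerned site pooling (SAP Section 6.2), and Addendum 1 removed it.

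**The concern.** The Cox partial likelihood assumes that event times can be ordered. When many events share a time, the software needs a rule, and the rules give different answers. Here ties are certain: several hundred subjects per comparison and no more than seven event times. The Breslow rule keeps every subject removed on a day in the risk set for all of that day's removals, which pulls the estimate toward no effect. Efron's rule largely corrects this.

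At stake are the retention hazard ratio and its interval. This is the plan's only time-to-event view of retention, which the study objective mentions. If the rule is left open, the estimate depends on a software setting that nobody chose in advance.

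**Working it through.** The documents give no hazard ratio, event count or power for retention, so there is no stated figure to reproduce.

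**Inputs from the documents.** Sample sizes are 225 per lofexidine arm and 150 on placebo (Protocol Section 10.2). Times are Days 1 to 7, with completers censored on Day 7 (Change 12). Tests are two-sided at 0.05 (SAP Section 6.14).

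**Assumptions.** Placebo completion c is 20% to 70%. The true hazard ratio θ is 0.50 to 0.80. Hazards are proportional in continuous time. There is no sex effect.

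**Closed form, flat hazard.** Let H = −ln(c)/7 be the daily placebo hazard. The daily removal probabilities are p0 = 1 − exp(−H) on placebo and p1 = 1 − exp(−θH) on lofexidine. For one tied day with n0 and n1 at risk and d0 and d1 removed, the Breslow score equation is d1 = (d0 + d1)·n1·e/(n0 + n1·e). Its solution is e = (d1/n1)/(d0/n0). With a flat hazard every day has the same expected ratio, so Breslow estimates p1/p0, a daily risk ratio, instead of θ. Shrinkage of the log hazard ratio is 1 − ln(p1/p0)/ln θ. With θ = 0.60:

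| Placebo completion | H | p0 | p1 | p1/p0 | Shrinkage |
|---|---|---|---|---|---|
| 70% | 0.0510 | 0.0497 | 0.0301 | 0.606 | 2.0% |
| 50% | 0.0990 | 0.0943 | 0.0577 | 0.612 | 3.8% |
| 35% | 0.1500 | 0.1393 | 0.0861 | 0.618 | 5.8% |
| 30% | 0.1720 | 0.1580 | 0.0981 | 0.621 | 6.6% |
| 20% | 0.2299 | 0.2054 | 0.1289 | 0.627 | 8.7% |

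At 20% completion with θ = 0.80, p1 = 1 − exp(−0.80 × 0.2299) = 0.1680 and p1/p0 = 0.818. The shrinkage is 1 − ln(0.818)/ln(0.80), or 9.9%.

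**How many ties.** Mean removals per day are [150(1 − c) + 225(1 − c^θ)]/7. With θ = 0.60 this is (45.0 + 43.4)/7 = 12.6 at 70% completion and (120.0 + 139.3)/7 = 37.0 at 20%.

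**Simulation, flat hazard.** Breslow and Efron were fitted to the same simulated trials, 500 per scenario. Shrinkage relative to Efron was 2.1%, 4.0%, 5.9%, 6.4% and 8.5% at 70%, 50%, 35%, 30% and 20% completion, in line with the closed form. At θ = 0.60 and 20% completion, Breslow gave 0.62 and Efron 0.59, with mean |z| 3.81 and 4.16. Over θ = 0.60 to 0.80 and completion 70% to 20%, a paired rerun gave shrinkage of about 2% to 11% and a power loss of about 1 to 9 points.

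**Simulation, other hazard shapes.** There were 600 runs per scenario; the rows below have θ = 0.65. Shrinkage relative to Efron is 1 − (100 − aB)/(100 − aE), where aB and aE are the percentage attenuations of the log hazard ratio against the true value.

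| Hazard | Placebo removal | Breslow HR | Efron HR | Shrinkage | Power, Breslow vs Efron |
|---|---|---|---|---|---|
| Flat | 30% | 0.666 | 0.660 | 1 − 94.5/96.4 = 2.0% | 50.2% vs 51.2% |
| Flat | 70% | 0.667 | 0.648 | 1 − 93.9/100.6 = 6.7% | 87.0% vs 91.2% |
| Front-loaded | 30% | 0.669 | 0.657 | 1 − 93.4/97.4 = 4.1% | 49.5% vs 52.7% |
| Front-loaded | 70% | 0.696 | 0.657 | 1 − 84.2/97.5 = 13.6% | 80.0% vs 87.7% |

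The widest gap was front-loaded removal at 70% with θ = 0.80: 1 − 86.5/101.8 = 15.0%, and power 30.8% versus 41.5%. Across all shapes, Breslow was nearer 1 than Efron in 90% to 100% of runs in every scenario.

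**Coverage and false positives.** With exponential times and θ from 0.60 to 1.0, Breslow 95% intervals covered the true value in about 94% to 98% of runs. Rejection under θ = 1 was 3.1% to 4.5%.

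**The case against.** A reader might infer that the plan, run as written, produces a biased result on part of the primary objective, with an unreliable interval. The documents do not support that reading, for four reasons.

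- The plan is silent on ties. It does not choose Breslow: SAP Section 6.1 names SAS but no Cox procedure or option. That the SAS default is Breslow is outside knowledge, and some other packages default to Efron.
- Retention is in the objective, but this Cox analysis is tertiary, unadjusted and outside the four-step testing sequence, and its hazard ratio is labelled descriptive. The controlled endpoint closest to retention is completion status, tested by logistic regression, where ties play no part. The Kaplan-Meier curves and daily tabulations are unaffected too.
- The interval holds its coverage, and the error runs against lofexidine, so it cannot create a false claim of benefit.
- The larger shifts need low completion or early, concentrated removal. An estimate of 0.63 for a true 0.60 belongs to 20% placebo completion, the extreme of the range.

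All four stand, and they keep the point minor. They do not remove it. The tie rule measurably changes the estimate, and the SAP fixes comparable details elsewhere: the covariance fallback order, the random seeds, and a non-convergence fallback for this same Cox model.

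**Conclusion.** The point holds as a minor, conditional one. The whole-day scale, the ceiling of seven values and the missing tie method are facts of the documents. The attenuation follows only if Breslow is used. It is then about 2% of the log hazard ratio at 70% placebo completion and about 10% at 20%, under a flat hazard, with about 1 to 9 points of power lost. It reaches 12% to 15% if 70% of placebo subjects are removed and most of them leave in the first days. The direction toward 1 was the same in every scenario on average; the size rests on assumed completion rates, hazard ratios and hazard shapes. No confirmatory conclusion changes.

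**What to change.** Add one phrase to the retention text of SAP Section 6.11: the Cox model uses Efron's method, or the exact continuous-time likelihood, for tied times. A complementary log-log model by study day, with day, treatment and sex, is an equally good choice. It targets the same hazard ratio, because ln(1 − p1)/ln(1 − p0) = θ under grouped proportional hazards.

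If exact ties are chosen, say that the discrete logistic form is not meant. That form estimates a daily odds ratio. At 20% completion and θ = 0.60 this is (0.1289/0.8711)/(0.2054/0.7946) = 0.57, a different quantity.

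The cost is one software option. The endpoint, population, censoring rule and estimand stay as they are. If Efron was intended all along, writing it down settles the matter.

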## 14.6 Concomitant Therapy

If the subject is admitted to the inpatient study unit the day before Baseline (i.e., Day -1), a single dose of a short-acting opioid (e.g., morphine) may be administered if needed to keep the subject reasonably comfortable; however, the administration may not occur after 8 PM on Day -1.

The concomitant medications or therapies listed below are permitted during Days 1-7 and Days 8-14 of the study.

1. Multivitamins ( $\leq 1$  tablet orally, administered daily at 9 AM).
2. Guaifenesin (for cough) ( $\leq 2$  teaspoons orally every 2 hours, as needed [PRN]).
3. Alumina, Magnesia, and Simethicone (for emesis and nausea) ( $\leq 30$  mL orally every 4 hours, PRN).
4. Dioctyl sodium sulfosuccinate (for constipation) ( $\leq 100$  mg orally every 8 hours, PRN).
5. Psyllium hydrocolloid suspension (for constipation) ( $\leq 1$  tablespoon orally every 12 hours, PRN).
6. Bismuth sulfate (Pepto-Bismol®) (for diarrhea) ( $\leq 6$  doses of 30 mL orally every 24 hours, PRN).
7. Acetaminophen (for headache, muscle aches, or other discomfort) ( $\leq 4$  doses of  $\leq 650$  mg orally every 24 hours).
8. Zolpidem (for insomnia) ( $\leq 10$  mg orally, PRN, may repeat 1 time if administered before 5:00 AM (i.e., 3 hours before the first morning dose of lofexidine or placebo). Zolpidem must not be administered before 11:00 PM (which is the time of the last daily dose of lofexidine or placebo).
  - 8a. Note: A short-acting benzodiazepine (e.g., oxazepam) may be used ad libitum for insomnia during the second part of the study (i.e., Days 8-14).
9. Nicotine replacement therapy (patch, inhaler, gum, nasal spray).

All other medications must be approved by the Sponsor's Medical Monitor before administration. If a subject requires any other medication for intolerable nausea and emesis (including a prescription opioid or non-opioid or an over-the-counter opioid or non-opioid) other than alumina, magnesia and simethicone, the subject will be discontinued from the study and given appropriate treatment according to the standard of care (see [Section 14.5.1](#)).

All medications taken will be recorded in the subject's source document and eCRF along with dose, dates of administration, and reason for use.

Psychosocial therapy (e.g., art, music, group sessions) will be allowed per standard of care at individual study sites. Acupuncture, however, will not be allowed. All therapies will be recorded in the subject's source document and eCRF.

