#### 17.2.8.6 *Concomitant Medication Analysis*

For each of Days 1 to 7, each subject's number of concomitant medication doses taken will be treated as a continuous variable. Descriptive statistics will be provided on the as-observed data on each study day. In addition, least squares means and p-values comparing each treatment to placebo will be obtained with the same methods used for SOWS-Gossop on Days 1, 2, 3, 4, 5, 6, and 7. Types of data transformation, if any, to be used before mixed effects modeling, will be specified in the SAP.

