Time to removal from study treatment is defined as the last study day on which the subject received treatment. The time for subjects who complete some but not all treatment on Day 7 will be Day 7, uncensored. Subjects who complete all treatments on Day 7 will be censored at Day 7. This endpoint will be summarized descriptively for each combination of treatment group and gender with Kaplan-Meier curves and tabulations of the number and percentage of subjects newly removed from receiving study treatment on each of study Days 1 to 7. Each Lofexidine dose group will be compared inferentially to placebo with a Cox proportional hazards regression model of time to removal from study, including covariates for treatment, gender and site. If the Cox proportional hazards model does not converge, then the covariates gender and site will be dropped from the model and the Cox proportional hazards regression model will be stratified by gender and site instead. The estimated hazards ratio will be reported as a descriptive measure along with the associated 95% confidence interval.

Concomitant Medication Analysis

For each of Days 1 to 7, each subject's number of concomitant medication taken will be treated as a continuous variable. Descriptive statistics will be provided on the as-observed data on each study day and also overall study days.

Status of Detoxification on Day 7 or Early Termination as Assessed by the Site Investigator

Descriptive statistics (numbers and percentages) on the status of detoxification (successful/unsuccessful) as assessed by the Site Investigator at Day 7 or early termination will be presented by treatment group overall and by gender within treatment group.

COWS AUC (1-7)

COWS AUC (1-7) will also be analyzed using a modelling approach analogous to the modelling of SOWS-Gossop AUC (1-7). While the functional form of the time course for SOWS-Gossop is based on historical data, the functional form of the time course for COWS will be based on the data from this study.

In addition, COWS will be analyzed using a mixed model repeated measures (MMRM) model in the same way as detailed for the sensitivity analysis of the primary endpoint with baseline COWS (based on same functional form for primary analysis) as a covariate.

Assessment of effectiveness

Summary statistics will be provided by treatment day (overall and by gender) over days 8-14 (Open Label Phase):

- SOWS-Gossop
- OOWS-Handelsman
- MCGI (Subject and Rater)
- VAS-E

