Only days when the patient was taking active treatment will be considered. Days after active administration will be disregarded.

For the calculation of the daily number of medications taken, the number of distinct coded drug names via the WHO dictionary will be used rather than verbatim terms.

Justification

To make the definitions within this analysis clearer.

Change 14

Section 6.13 Safety analysis

Add the text in bold

All subjects who receive at least dose one of study medication will be included in the analysis of safety.

Safety measures will be summarized for the following subject cohorts for the open label phase:

- \neq All treated subjects;
- ≠ Treated subjects without urinary evidence of illicit drug use (i.e. any positive result in the urine drug screen during the open-label phase, including all categories); and
- ≠ Treated subjects with urinary evidence of illicit drug use (may be further subdivided by type of illicit drug used).

Safety measures will only be summarized for all treated subjects for the double blind phase.

Extent of exposure

Extent of exposure will be described by whether the subject took the trial medication and the number of days exposure to double-blind study medication (last date of double-blind medication minus first date of double-blind medication + 1). Average daily dose of double-blind study

Effective: 24-Dec-2014

Page 13 of 29

medication will also be calculated **by number of doses/exposure (days)**. Exposure to open-label medication will also be calculated as last date of open-label medication – first date of open-label medication + 1. No allowance will be made for breaks in therapy in the exposure calculations. Average daily dose of open-label study medication will also be calculated. If the date of last dosing is completely missing for the trial medication then the date of last dosing will be taken for analysis purposes as the date the medication was last dispensed. As there are no open-label dosing dates recorded on the eCRF, dates of visits will be used instead. In particular it will be assumed that open-label dosing starts one day after double-blind dosing ceases.

Justification

To make the definitions clearer.

Change 15

Section 6.13 Safety analysis

Vital Signs During the Double-Blind Phase

The following text was amended:

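### The SAP replaces the protocol's daily dose count of concomitant medication with a count of distinct drug names, drops the comparison with placebo, and declares neither change

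*SAP*

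**What the plan says.** Protocol section 17.2.8.6 sets the measure for each of Days 1 to 7: "each subject's number of concomitant medication doses taken will be treated as a continuous variable". Besides descriptive statistics, it plans a comparison: "least squares means and p-values comparing each treatment to placebo will be obtained with the same methods used for SOWS-Gossop". Protocol section 17.2.6 lists this analysis as tertiary/exploratory.

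The June 2014 SAP, section 6.11, changes the measure to "each subject's number of concomitant medication taken will be treated as a continuous variable". It keeps only a description: "Descriptive statistics will be provided on the as-observed data on each study day and also overall study days". No least squares means or p-values remain.

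Addendum 1, Change 13, adds two rules. For the daily count, "the number of distinct coded drug names via the WHO dictionary will be used rather than verbatim terms". For the days that count, "Only days when the patient was taking active treatment will be considered"; later days are disregarded. Its stated reason is to make the definitions clearer.

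SAP section 6.14 declares changes to protocol sections 17.2.7, 17.2.8.1, 17.2.8.2, 17.2.8.3, 17.2.8.4 and 17.2.8.5. Section 17.2.8.6 is not among them. Addendum 2 does not return to the subject.

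**The concern.** The permitted products in protocol section 14.6 are mostly taken as needed and may be repeated within a day. Some treat symptoms that the SOWS-Gossop scores: acetaminophen for aches, the antacid for nausea (the feeling-sick item) and zolpidem for insomnia. If the arms differ in how much of these they take, a reader of the SOWS-Gossop result would want to know by how much. The protocol's dose count, compared with placebo, was designed to show that. A count of drug names without a comparison shows much less of it.

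The reporting matters too. Section 6.14 declares changes as small as moving gender from a stratum to a covariate in the Cox model, yet it is silent on a change of variable and the loss of a planned test. Change 13 presents a new variable as a clarification.

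**Working it through.** The documents give no assumption or figure for concomitant medication use, so there is no stated number to reproduce. The check sets the texts side by side and then compares the two measures under the protocol's own limits.

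**Step 1: where each element was lost**

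| Element | Protocol 17.2.8.6 | SAP 6.11 (June 2014) | Addendum 1, Change 13 |
|---|---|---|---|
| Measure | Doses per day | Medications per day | Distinct coded drug names per day |
| Comparison with placebo | LS means and p-values | None | None |
| Days | 1 to 7 | 1 to 7 | Only days on active treatment |

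Doses and the comparison both go in SAP 6.11. Change 13 fixes the name count and adds the day rule.

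**Step 2: inputs for the two measures**

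Daily limits from protocol section 14.6, reading an interval of h hours as 24/h doses:
- multivitamin 1
- guaifenesin 24/2 = 12
- antacid (alumina, magnesia and simethicone) 24/4 = 6
- dioctyl sodium sulfosuccinate 24/8 = 3
- psyllium 24/12 = 2
- bismuth 6
- acetaminophen 4
- zolpidem 2 (one dose, one repeat)

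Nicotine replacement and the Days 8-14 benzodiazepine are left out. Each product is assumed to code to one drug name.

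**Step 3: formulas**

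Let n(k) be the doses of product k in a day. The protocol's measure is D = sum of n(k). The SAP's measure is M = number of products with n(k) of at least 1.

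**Step 4: results**

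| Day's use | D (doses) | M (names) |
|---|---|---|
| Acetaminophen 4, antacid 6, bismuth 6 | 4 + 6 + 6 = 16 | 3 |
| One dose of each of these three | 3 | 3 |
| Acetaminophen 4, antacid 6, zolpidem 2 | 4 + 6 + 2 = 12 | 3 |
| One dose each of acetaminophen, antacid, zolpidem | 3 | 3 |
| Acetaminophen 4, bismuth 6 | 4 + 6 = 10 | 2 |
| All eight products at their limits | 1 + 12 + 6 + 3 + 2 + 6 + 4 + 2 = 36 | 8 |

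M cannot separate 16 doses from 3. The same holds when only products listed for SOWS-Gossop symptoms are used: 12 doses and 3 doses both give three names. The ranking can even reverse: 10 doses score two names, while single doses of acetaminophen, antacid and zolpidem (3 doses) score three. These are extremes allowed by the limits, not expected use.

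**Step 5: the day rule**

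SAP section 6.9.1, step 4, uses active treatment for the two lofexidine doses as opposed to placebo. Read that way, Change 13 would leave placebo subjects with no eligible days. Against this, SAP section 6.5 summarizes by group including placebo, Change 13 still speaks of each subject on Days 1 to 7, and its next sentence refers to days after administration ends. Double-blind study treatment in every arm is the more plausible meaning.

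**The case against.** The strongest case on the other side has five parts.

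- **The count still carries information.** It separates no use from any use and shows how many different drugs were taken. SAP section 6.13 also tabulates concomitant drugs by class, name and treatment group. This stands, but neither measures amount per day or compares it with placebo.
- **The eCRF may not support a dose count.** Protocol section 14.6 requires entries in the "eCRF along with dose, dates of administration, and reason for use", which is not explicitly the number of administrations. For study drug, section 13.2.1 asks for the date and time of each dose; for concomitant drugs no such rule appears. Addendum 1, Change 14, notes that open-label dosing dates were not on the eCRF at all. This stands: that dose counts can be derived is an assumption. If they cannot, section 6.14 is the place to say so.
- **Not every permitted product bears on the SOWS-Gossop.** Bismuth is for diarrhea, guaifenesin for cough, and two others for constipation; none is listed for cramps. This limits the link to aches, nausea and insomnia. Step 4 shows the same loss of information with those products alone.
- **The active-treatment wording is only loose.** A reader might infer that the placebo arm is removed. The surrounding text does not support that; it supports only a wording correction.
- **The endpoint is exploratory.** It lies outside the testing sequence in SAP section 6.12, and the SAP does not adjust the SOWS-Gossop analysis for concomitant use. This stands in full.

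**Conclusion.** The point holds as an undeclared departure in one tertiary analysis. The dose count and the comparison with placebo were lost in SAP section 6.11, Change 13 settled on distinct names, and section 6.14 neither lists nor justifies the departure. The resulting measure does not track the amount used: under the section 14.6 limits the same score of three covers anything from 3 to 16 doses in the examples above.

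Two stronger readings are tempting and not supported. One is that the analysis no longer captures use of symptom-relief medication; it still captures any use and the number of different drugs, and the protocol calls these products permitted concomitant medications, not rescue. The other is that the SOWS-Gossop treatment difference is biased. The documents give no data on use by arm, so neither the direction nor the size of any imbalance is known. The primary and secondary conclusions are unaffected.

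The conclusion assumes that each product codes to one name and that the section 14.6 intervals can be read as daily maxima. The remedy also assumes that the eCRF records permit a daily count.

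**What to change.** In SAP section 6.11 and Addendum 1, Change 13:

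- Restore doses per day as the measure, provided the eCRF dose and date records allow a daily count. If they do not, state that in section 6.14 as the reason for the change.
- Compare each lofexidine dose with placebo by the by-day MMRM that the SAP now uses for the other daily endpoints, without a baseline covariate, as Change 11 already does for the MCGI and VAS-E. Section 6.14 has replaced the by-day pattern-mixture method to which protocol section 17.2.8.6 refers, so the model needs naming. State any transformation, which the protocol leaves to the SAP.
- Keep distinct drug names as a secondary description.
- Replace the active-treatment wording with double-blind study treatment (lofexidine or placebo).
- List any remaining departure from protocol section 17.2.8.6 in section 6.14, with its reason.

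The cost is SAP wording and one more exploratory table. A limitation remains: later-day data come only from subjects still on treatment, so comparisons on those days depend on who stayed in each arm and should be read that way.
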